PROTOCOL FULL TITLE: A randomised, balanced, double-blind two-way crossover design study to evaluate the effects of SRC kinase inhibitor, Saracatinib, on brain activity associated with visual processing in patients with Parkinson's disease Psychosis.

Protocol Short Title/Acronym: SRC inhibition as a potential target for Parkinson's disease psychosis- SCRIPT

Trial Identifiers

REC Number – **[Awaiting further information]**

Co-Sponsors: King's College London & Kings College Hospital NHS trust

Chief Investigator

Name: [name]

Address: Department of Neuroimaging, Institute of Psychology, Psychiatry and Neuroscience, King's College London, [name]

[contact]

Email: [contact]

Name and address of Co-Investigator(s), Statistician, Laboratories etc

Name: [name] [name]

Address: Department of Old Age Psychiatry, Institute of Psychiatry, Psychology and Neuroscience, King's College London, [name]

Telephone:

Fax:

Email: [contact]

Name: [name]

Address: Dept. Basic and Clinical Neuroscience, The Maurice Wohl Clinical Neuroscience Institute, King's College London, [name]

Telephone:

Fax:

Email: [contact]

Name: [name]

Address: Department of Old Age Psychiatry, Institute of Psychiatry, Psychology and Neuroscience, King's College London, [name]

Telephone:

Fax:

Email: [contact]

1. Study Synopsis

Title of clinical trial	A randomised, balanced, double-blind two-way crossover design study to evaluate the effects of SRC kinase inhibitor, Saracatinib, on brain activity associated with visual processing in patients with Parkinson's disease Psychosis.
Protocol Short Title/Acronym	SRC inhibition as a potential target for Parkinson's disease psychosis- SCRIPT
Trial Phase if not mentioned in title	
Sponsor name	King's College London (KCL)/ King's College Hospital (KCH)
Chief Investigator	[name]
REC number	
Medical condition or disease under investigation	Parkinson's disease Psychosis
Purpose of clinical trial	To test the effects of Saracatinib on brain activity associated with visual processing in Parkinson's disease psychosis.
Primary objective	To examine the effects of Saracatinib on brain activity associated with the visual recognition task in PD psychosis.
Secondary objective (s)	
Secondary:
 
 • To examine the effects of Saracatinib on brain activity associated with visual processing in patients with PD psychosis. • To examine the effects of Saracatinib on brain connectivity within the default mode network in patients with PD psychosis. 
Exploratory:
 
 • To examine the effects of Saracatinib on brain connectivity with the inferotemporal cortex in patients with PD psychosis. • To examine the effects of Saracatinib on brain activity measured with EEG during a mismatch negativity paradigm in patients with PD psychosis. • To test a prediction error model for the effects of Saracatinib on brain activity measured with EEG during a mismatch negativity paradigm in patients with PD psychosis. • To examine the effects of Saracatinib on standard questionnaires of motor and non-motor experiences in patients with PD psychosis.

Trial Design
	
A Randomised, balanced double blind two-way cross-over design.

Endpoints
	
Primary Endpoint:
 
 • Difference between study drug and placebo in BOLD activity in the ventral visual stream during visual recognition vs. the control task measure using fMRI. 
Secondary:
 
 • Difference between study drug and placebo in BOLD activity in the occipito-temporal region during the visual processing task (Kanisza illusion). • Change in Mismatch negativity (MMN) in microvolts (mV) and connectivity with the posterior cingulate hub of the default mode network. 
Exploratory:
 
 • Seed-based connectivity from the Regions Of Interest (ROI) within the inferotemporal cortex. • Difference between study drug and placebo in MMN amplitude at FZ on EEG. • Test a prediction error model for the effects of Saracatinib on brain activity during a mismatch negativity paradigm on the EEG. • Difference between study drug and placebo in Factor summary score on the scales for assessment of positive symptoms in Parkinson’s disease (SAPS-PD) and the Neuropsychiatric Inventory (NPI).

Sample Size
	
30 participants with PD psychosis to be enrolled for 26 completers.


Summary of eligibility criteria
	
To be considered eligible for this study participants must:
 
 1. Understand the study procedures and agree to participate by providing written informed consent. 2. Have a confirmed diagnosis of Parkinson’s disease using internationally accepted UK brain bank criteria. 3. Be male or female 4. Be right handed 5. Aged 40 years or over 6. Be judged to be in good health by the investigator, based on clinical evaluations including laboratory safety tests, medical history, physical examination, 12 lead ECG and vital signs measurements performed at screening and prior to administration of the initial dose of study drug. 7. Have a score of at least 22 in the Montreal Cognitive Assessment (MoCA). 8. Have a diagnosis of idiopathic PD 9. Have a combined score of at least 6 or an individual score of at least 4 on the neuropsychiatric inventory (NPI [20]) 23 items A (delusions) and/or B (hallucinations).

PROTOCOL SCRIPT

Study drug, dosage, and route of administration	AZD0530 (saracatinib) oral dose 100mg administered as two 50mg tablets
Active comparator product(s)	N/A
Maximum duration of treatment of a Subject	14 days (+/- 2 days)
Version and date of protocol amendments	V 2.2 23/08/18

2. Background & Rationale

2.1 Parkinson's disease psychosis and visual hallucinations

Parkinson's disease (PD) is a neurodegenerative condition which has a 1% prevalence in the over 60s and also affects young adults. As well as motor symptoms such as akinesia or rigidity, many patients also experience non-motor symptoms of which psychosis is the most common (Chang and Fox, 2016). Psychosis in Parkinson's disease has been identified as a spectrum of illusions, visual hallucinations, auditory hallucinations and delusions that occur throughout the course of the disease (Ffytche et al., 2017). Current treatments for Parkinson's disease psychosis include atypical antipsychotics such as quetiapine, clozapine and pimavanserin (a 5-HT_{2a} inverse agonist). Pimavanserin has recently been approved in the USA as a PD psychosis treatment; it has been shown to have an overall effect on reducing hallucinations as a whole, but not on visual hallucinations specifically. Functional neuroimaging evidence confirms dysfunctional ventral visual pathway activity in PD psychosis with altered metabolism, blood flow and brain activation following visual stimulation (Chang and Fox, 2016). Outside of the ventral visual pathways, two imaging studies in PD patients with visual hallucinations have shown altered connectivity within the default mode network, a brain system implicated in many neuropsychiatric conditions, pointing to more widespread abnormalities (Chang and Fox, 2016). Structural imaging studies show some atrophy within the ventral visual pathways, but also implicates brain regions outside of visual processing areas, including parietal, frontal, and cerebellar and hippocampal regions (Ffytche et al., 2017). Some authors have argued that the atrophy is independent of the hallucinations (Meppelink et al., 2011). Together, these studies fit with previously proposed models of PD psychosis that suggest that it is caused by both disrupted bottom-up processing of sensory information and dysfunctional top-down influences on perceptions.

2.2 The Serotonergic system and current treatments

Although many treatments for psychosis unrelated to Parkinson's disease are centred on dopaminergic therapies, post-mortem and *in-vivo* human studies have shown loss of striatal and extra-striatal serotonin markers in the course of PD, suggesting the involvement of the serotonergic system in PD (Politis and Niccolini, 2015). Furthermore, the serotonin system has also been implicated in PD psychosis. *In vivo*, [18F]-setoperone PET studies showed increased 5-HT_{2a} receptor binding in people with PD with visual hallucinations in the ventral visual pathway (Ballanger et al., 2010). A post-mortem study showed increased [3H]-ketanserin binding in the inferolateral temporal cortex in people with visual hallucinations compared to PD patients without visual hallucinations (Huot et al., 2010). Although pimavanserin has been shown to reduce hallucinations overall, it does not affect visual hallucinations specifically. Even though the serotonergic

dysfunction underpinning Parkinson’s disease psychosis is not fully understood, animal studies with psychedelics have pointed to the dimerisation of the 5-HT_{2A} and mGlu₂ receptors and the over recruitment of specific downstream signalling pathways. Src kinase inhibition is a potential mechanism for blocking the hallucinogenic effects of 5-HT_{2A} receptor agonism. Src kinase inhibitor, Saracatinib, has shown to reduce the intensity of the psychedelic effect induced by psilocybin (a naturally occurring psychedelic found in psilocybe mushrooms (Byock, 2018)) and attenuate social cognition and brain changes in healthy volunteers.

We will test the effects of Saracatinib on brain activity associated with visual processing using a visual processing task, known to be sensitive to 5-HT_{2a} receptor stimulation in previous studies with psilocybin (Carter et al., 2004), and a visual recognition task (Meppelink et al., 2009) with known sensitivity to PD psychosis, both scanned using the latest implementation of multi-echo blood oxygen level dependent (BOLD) functional Magnetic Resonance Imaging (fMRI). Resting state fMRI is a type of functional neuroimaging that allows the assessment of intrinsic correlations within known brain networks. Since alterations in resting state fMRI within the default mode network (a network of regions in the brain that have been demonstrated to have a role in image production (Catani et al., 2013)) have been shown in PD psychosis this will be an important tool to uncover potential ‘non-visual’ mechanisms modulated by Saracatinib.

2.3 Rationale for the study design

We aim to conduct a double-blind crossover design study, looking at the effects of Saracatinib and placebo treatment on 26 patients who have PD with psychosis. Existing data shows that 10 days of dosing with Saracatinib will achieve a steady state level that is known to be well tolerated in people with Alzheimer’s disease (Nygaard et al., 2015). Therefore, participants will be given an oral dose of 100mg of Saracatinib as two 50mg tablets to be taken once daily for 14 days. Participants will return to the clinic on day 14 for their final dose of Saracatinib, fMRI and EEG scans, cognitive assessments (described in section 6.2), physical examination and blood screen. There will be a minimum 2-week washout between treatment arms to avoid potential carry over effects. A cross-over design was chosen for this study to minimize the potential impact of inter-subject variability on the ability to detect a treatment effect of Saracatinib, as each subject serves as his/her own comparator. A placebo control is standard in the evaluation of novel therapeutics for neuropsychiatric disorders.

The aim of the current study is to use neuroimaging combined with psychopharmacology to provide evidence that a putative new treatment approach can modulate abnormal visual cortex activation in patients with PD psychosis. If positive, this proof of mechanism study would provide a strong platform to pursue symptom modification studies with Saracatinib.

Saracatinib is considered to be safe and well tolerated by healthy volunteers in doses up to and above the dose used in this study (100mg for 14 days (+/- 2 days)) this dose (100mg) is also well tolerated by patients with Alzheimer's disease (Nygaard et al., 2015). The most common side effects reported in multiple dose healthy volunteer studies in doses lower than 125mg were headache, papular rash, upper respiratory tract infection, loose stools, and myalgia.

2.3.1 Dose justification

An oral dose of 100mg of Saracatinib (two 50mg tablets) will be administered during the study period. Previous data from Nygaard et. al. in 2015 shows that doses between 50mg to 125mg are well tolerated in human participants with Alzheimer's disease. 100mg was the lowest dose that inhibited src-kinase activity in the periphery and was clearly detectable in the CSF. The study states that substantial nervous system penetration with an oral dose is achieved between 100 to 125mg, although at 125mg there were some safety and tolerability issues (Nygaard et al., 2015). Therefore, we have selected 100mg given o.d. for 14 days (with or without food) to achieve steady state plasma levels.

3. Trial Objectives and Design

3.1. Trial Objectives

Primary:

- To examine the effects of Saracatinib on brain activity associated with the visual recognition task in patients with PD psychosis.

Secondary:

- To examine the effects of Saracatinib on brain activity associated with visual processing in patients with PD psychosis.
- To examine the effects of Saracatinib on brain connectivity within the default mode network in patients with PD psychosis.

Exploratory:

- To examine the effects of Saracatinib on brain connectivity with the inferotemporal cortex in patients with PD psychosis.
- To examine the effects of Saracatinib on brain activity measured with EEG during a mismatch negativity paradigm in patients with PD psychosis.
- To test a prediction error model for the effects of Saracatinib on brain activity measured with EEG during a mismatch negativity paradigm in patients with PD psychosis.

- To examine the effects of Saracatinib on standard questionnaires of motor and non-motor experiences in patients with PD psychosis.

3.1.1 Primary endpoints

- Difference between study drug and placebo in BOLD activity in the ventral visual stream during visual recognition vs. the control task measure using fMRI.

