3.2 Trial Design

This will be a balanced double-blind two-way crossover design study looking at the effects of Saracatinib on brain activity associated with visual processing in patients with Parkinson's disease psychosis. This study will be carried out at a single site in the UK.

Approximately 30 patients for 26 completers with Parkinson's disease psychosis will be required to attend the study site for 5 visits; the initial screening visit, and two visits for each of two study periods. On day 1 of each study period they will attend for baseline cognitive assessments to provide a profile for the patient and will receive their first dose

of study medication (Saracatinib/placebo). They will take a dose of the medication at home every morning for the following 12 days (Days 2-13) and return to the study site on day 14 (+/- 2 days) for dosing and have their day 14 assessments performed (fMRI, EEG, Kanisza task, Meppelink task, NPI, SAPS-PD and physical examination). The two study periods will be separated by a washout period of at least 2 weeks. Approximately 14 days after their day 14 visit for study period 2 they will receive a telephone follow up call.

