3.3 Trial Flowchart

Study days	Screening	Study period 1 and 2 ¹												Early termination visit ²
		Day 1- Baseline and Placebo/drug dose					Day 2-13	Day 14- Scanning and assessment day					Follow up	
		Hours						Hours						
	Pre-Dose	0	1	2	3		Pre-Dose	0	1	2	3	4		
Patient consent	X													
Physical examination	X	X						X					X	X
Neurological examination	X	X						X					X	X
Vitals ³	X	X		X	X	X		X					X	X
12- lead ECG	X	X						X						X
Oral dose of drug ⁴			X				X		X					
NPI ⁵	X	X						X						
MoCA	X	X						X						
SAPS-PD	X	X						X						
Lab safety blood and urine tests ⁶	X	X											X	
Hepatitis screen	X													
Urine drug screen	X	X						X						
Pharmacokinetic blood sample ⁷		X						X			X	X		
Non-motor symptoms ⁸		X												
SCOPA-MOTOR ⁷		X												
PD sleepiness scale ⁷		X						X						

¹ There will be a minimum 14-day washout period between study periods

² This visit will only take place if a participant decides to discontinue study treatment

³ Vitals will consist of semi recumbent blood pressure, heart rate, temperature, and respiratory rate.

⁴ 100mg of Saracatinib or placebo

⁵ To ensure that the inclusion criteria have been met. Minimum combined score of 6 in hallucinations and delusions section.

⁶ For females of child-bearing potential.

⁷ To measure the levels of Saracatinib/Placebo in the blood at baseline and scanning day.

⁸ Profiling assessments- only applicable to period one.

PROTOCOL SCRIPT

Word reading (WTAR) ⁷		X														
Verbal fluency ⁸		X														
Months reversed ⁹		X														
NEVHI ⁸		X						X								
Clinical impression of severity index ⁸		X														
fMRI											X					
EEG												X				
Kanizsa illusion ¹⁰											X					
Meppelink task (visual pop-out) ⁹											X					
Visual Analogue scales								X								
PDQ		X											X			
EQ		X											X			
Dispense study medication						X										
Telephone call							X							X		X
Adverse event monitoring																

⁹ Profiling assessments- only applicable to period one

¹⁰ While in the MRI scanner.

4 Trial Medication

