study, baseline questionnaire and assessments will be carried out. These include the Non-motor symptoms, SCOPA-MOTOR, PD sleepiness, WTAR, verbal fluency, months' reversed, clinical impression of severity index and the NEVHI (assessments described in section 6.2). The recall period for each of the assessments will be adapted to when the visit is taking place. Following completion of the baseline assessments the participant will receive their first dose of study medication. Saracatinib/placebo will be administered followed by a 3 hour stay during which vitals will be assessed at regular intervals. A physical examination will take place prior to discharge. On discharge, medication will be provided to be taken for the following 12 days, confirmed by daily telephone contact.

Days 2 to 13

Patients will take a dose (two 50mg tablets) of study medication at home each morning. The study team will telephone the patient/their carer each day to confirm the medication has been taken and to assess for any adverse events.

Day 14 Scanning visit

On the 14th day participants will be asked to attend the research facility in the time window of 12-16 days after their first dose, given their last dose of the study medication and then at approximately 2 hours post dose will be scanned using BOLD fMRI whilst doing the Kanizsa task and the Meppelink task. After MRI scanning is complete participants will have mismatch negativity measured using EEG. They will also have the NPI, SAPD-PD, PD sleepiness scale, NEVHI, PDQ and EQ (details of the tasks and scans outlined in section 6.2 below).

Following this, participants will undergo a physical examination and assessment by the study physician, and they will also have blood sampling for pharmacokinetic/drug exposure levels. Participants will then be discharged provided there are no concerns. There will then be a minimum 14-day washout (+/- 2 days), after which they will return for day 1 of the second study period. All study procedures (apart from the profiling assessments) on days 1 through 14 will be repeated for study period 2.

Participants will be contacted by telephone between 10 and 14 days after their final visit to check for adverse events.

Early termination visit

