The scanning protocol will comprise a localiser to ensure a good positioning in the scanner, T1-weighted structural scan (to allow registration to a template), multi-echo resting state scan (for connectivity), Kanizsa illusion, the Meppelink task and a perfusion scan using pseudo-continuous ASL (to determine changes in neurovascular coupling caused by the drug).

Kanizsa Illusion

The Kanizsa task is a task that comprises of illusory contours which are perceived edges that 'bridge gaps between aligned luminance edges' but do not exist physically. The Kanizsa task is a task that used the perceived edges to give a direct comparison of the physiological response to illusory contours which may reveal information about object perception (Mendola et al., 1999). This task will take approximately 12 minutes.

Visual pop-out task (Meppelink task)

A visual task where objects, animals and people appear out of noise and participants must press a button when they recognise what it is. A previous study by Meppelink et. Al. reported that patients with visual hallucinations and Parkinson's disease had decreased activation of the lateral occipital cortex several seconds before image recognition compared to patients with PD but no psychosis and healthy controls (Meppelink et al., 2009). This task consists of 50 images appearing from noise and each video lasts for 30 seconds. In total, the task will take approximately 20 minutes.

Visual analogue scales of physical fatigue, mental fatigue and overall health

Visual scales ranging from 0-100 where the patient marks on the scale how they would rate their physical fatigue, mental fatigue, and overall health today.

PDQ

The Parkinson’s disease questionnaire is a quality of life questionnaire specific to Parkinson’s disease (Young et al., 2013). It is composed of 39 questions and participants are asked to read a statement and indicate on a scale of ‘Never’ to ‘Always or cannot do at all’ which applies best. The questionnaire assesses difficulties of daily living across 8 dimensions. The scale can provide a single figure that can be used to assess the overall quality of life related to health.

EQ-5D

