9.1 Sample Size

A group of approximately 30 with PD Psychosis will be enrolled in the study for 26 completers.

We used the results from (Meppelink et al., 2009), to estimate statistical power to detect the attenuation in the brain activity impairments prior to and during ‘pop-out’ recognition of degraded stimuli. This activity is reduced in those with PD psychosis with visual hallucinations compared to those without hallucinations. The signal reduction is greatest immediately before target detection or ‘pop-out’ in clusters with peaks in the occipital lobe and fusiform gyrus extending into the posterior lateral temporal lobes. The signal changes from the bilateral peaks in the fusiform gyrus were used for the power calculation. An effect size of 2/3 of that seen in Meppelink was used as a conservative estimate of the predicted change with Saracatinib (see below for justification of effect). For left fusiform prior to ‘pop-out’ the power calculation was for an effect size of 0.91 ($0.66 * 1.39$) and SD of 0.048 on the mean difference of 0.0462 requiring 15 patients with a power of 0.9 and alpha of 0.05, or 20 patients with alpha=0.01. The same calculation for the right fusiform gyrus gives a sample size of 13 patients for an effect size of 1.26 and alpha=0.01 (or a difference of 0.0595 with an SD of the difference of 0.046). Based on these calculations we propose to recruit 30 patients for at least 26 completers, with a primary endpoint of change in activity in the fusiform/posterior lateral temporal lobes. Drop-outs may be replaced at the discretion of the investigator.

For fMRI power calculations: A change in fMRI signal would indicate support for the modulation of the hypothesized mechanism. This is generally considered a valuable goal in proof of mechanism experimental studies. Understanding if the effect size of the fMRI signal change is clinically meaningful (i.e. likely to result in symptom improvement) would provide a stronger platform for translating findings for patient benefit and potentially aid outcome measure and dose selection. There are many examples of treatment studies in which fMRI changes are accompanied by symptomatic improvement. For example, in patients with psychosis (unrelated to Parkinson’s disease) and other

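### Does the undefined control task in the primary endpoint leave the trial with two different primary quantities?

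*Combined protocol and SAP*

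**What the plan says.** - **Endpoint.** The synopsis and 3.1.1 define the single primary endpoint as the difference between study drug and placebo in "BOLD activity in the ventral visual stream during visual recognition vs. the control task measure using fMRI".
- **What is scanned.** Section 3.2 lists the Day 14 assessments as "fMRI, EEG, Kanisza task, Meppelink task, NPI, SAPS-PD and physical examination". The flowchart in 3.3 has a row for the "Meppelink task (visual pop-out") task, and 6.1 says that participants "will be scanned using BOLD fMRI whilst doing the Kanizsa task and the Meppelink task". After the localiser and structural scan, 6.2.2 lists a "multi-echo resting state scan (for connectivity), Kanizsa illusion, the Meppelink task and a perfusion scan using pseudo-continuous ASL". None of these names a control task.
- **The recognition task.** Section 6.2.2 describes it as "A visual task where objects, animals and people appear out of noise and participants must press a button when they recognise what it is", with 50 images and 30-second videos. It mentions no control stimuli.
- **Sample size.** Section 9.1 uses the fusiform signal just before pop-out and proposes 26 completers "with a primary endpoint of change in activity in the fusiform/posterior lateral temporal lobes".
- **Analysis.** Section 9.3 takes a mean beta per hemisphere in a predefined ventral visual region, derived session by session and blind to treatment. The pop-out task gets a finite impulse response (FIR) model locked to detection, and the primary analysis uses the interval just before recognition. The group model has drug and session as fixed factors and subject as a random effect. An analysis plan defining the variables is to be final before unblinding.

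**The concern.** Section 3.1.1 read alone calls for recognition minus control. Section 9.3 read alone calls for the pre-recognition beta. If these are different quantities, they can give different primary results, and the choice between them should not be open once treatment is known. The comparator is also part of what the endpoint means: subtracting a control removes any additive drug effect on BOLD common to both conditions, whereas a beta without subtraction keeps it. The protocol seems aware of non-specific drug effects, since the perfusion scan is included "to determine changes in neurovascular coupling caused by the drug". In a proof-of-mechanism trial it matters whether a signal change belongs to recognition or to blood flow in general. A reader could therefore conclude that the endpoint names a condition that is never acquired, or that the analysis drops a contrast that the endpoint requires.

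**Working it through.** **1. The plan's own sample size.** Inputs from 9.1: left fusiform effect size d = 0.91, with N = 15 at alpha 0.05 and N = 20 at alpha 0.01; right fusiform d = 1.26, with N = 13 at alpha 0.01; power 0.9 throughout. Sidedness is not stated; two-sided is assumed. For a paired t-test, power = P(|T| > t(1 − α/2, n − 1)), where T is noncentral t with n − 1 degrees of freedom and noncentrality d√n.

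- d = 0.91, alpha 0.05: N = 15, as stated.
- d = 0.91, alpha 0.01: N = 22 against the stated 20. The section's own ratio 0.0462/0.048 = 0.9625 gives exactly 20.
- d = 1.26, alpha 0.01: N = 13, as stated.
- 26 completers, d = 0.91: power 0.994 at alpha 0.05 and 0.960 at alpha 0.01.

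The figures reproduce for the pre-recognition fusiform signal. They do not reveal whether the source effect sizes already include a baseline or control.

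**2. Do the sections conflict?** Sections 3.1.1, 9.1 and 9.3 agree on the task (recognition, or pop-out), the comparison (saracatinib against placebo) and the broad region (ventral visual stream, located in 9.1 and 9.3 around the fusiform and lateral temporal cortex). Sections 9.1 and 9.3 also agree on the interval before recognition. Only the comparator is left unstated.

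**3. Do the fixed factors exclude a contrast?** No. The analysis has two stages: a first-level model per session, then ROI values entered into the group model. A recognition-minus-control contrast would be computed in the first stage and would reach the second as one number per session and hemisphere. Drug and session are the right fixed factors with or without it.

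**4. Do the task lists show that no control is acquired?** No. They list runs. Section 6.2.2 does not enumerate the Kanizsa conditions, yet 9.3 refers to several. The same could hold for the pop-out task, for example with noise before recognition as baseline, although the protocol does not say so. Task length is not decisive: 50 × 30 s = 1,500 s = 25 minutes at full length, against a stated 20 or so. That counts against a separate added block, but not against a baseline within the videos.

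**5. Would subtraction deal with neurovascular coupling?** Not if the drug acts as a gain g on the response. With R the recognition response and C the control response, gR − gC = g(R − C), so the contrast is still scaled by g. Subtraction removes only an additive shared effect.

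**6. Can the consequence be sized?** Only by assumption. Suppose 9.1 is uncontrasted, the SD of the drug–placebo difference is equal in the two conditions, the drug has no effect in the control, and ρ is the correlation between the two drug–placebo differences. Then d = 0.91/√(2(1 − ρ)), and with n = 26:

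| ρ | d | power, alpha 0.05 | power, alpha 0.01 |
|---|---|---|---|
| 0 | 0.643 | 0.884 | 0.687 |
| 0.25 | 0.743 | 0.953 | 0.831 |
| 0.5 | 0.910 | 0.994 | 0.960 |
| 0.75 | 1.287 | >0.999 | >0.999 |

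The direction reverses at ρ = 0.5, and the documents give no ρ. A shift in the estimate likewise needs an invented share: if 25% or 50% of the 0.0462 difference were common to the control, the contrast would be 0.0462 × 0.75 = 0.0347 or 0.0462 × 0.50 = 0.0231. That assumption contradicts the one behind the table. These figures show what could be imagined; they do not show an effect in this trial.

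**The case for a change.** The strongest case for a change is that the comparator belongs to the definition of the primary endpoint and should not be left to a later document. The protocol uses the term in its endpoint statements only and never explains it. No task description supplies a candidate, and an FIR estimate depends on what serves as its baseline. Even the charitable reading, a baseline within the task, therefore has to be written down somewhere. The Kanizsa task does not fill the role, because it has its own secondary endpoint. Silence about a contrast that the endpoint names is itself a loose end, and tidying the wording would cost little.

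Most of this stands as description: the term is undefined, and 9.3 does not say whether the beta is contrasted with anything. What does not follow is that the plan analyses the wrong quantity, lacks power or invites choice after the results are known. Section 9.3 already provides for variable definitions to be settled before unblinding, and the ROI values are derived blind. The remaining choice is therefore made without sight of treatment. The case also identifies no stated rule that gives a wrong answer and no better method; it asks only that the sponsor record which comparator was meant.

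**Conclusion.** The concern rests on a real omission, but no change to the plan follows. Carrying out 9.3 as written gives a sound treatment comparison of the signal used for the sample size in 9.1: a blinded ROI beta before recognition, compared between saracatinib and placebo with session in the model. If the endpoint wording refers to a condition or baseline within the task, the contrast fits into the first-level stage without altering the group model. Naming it is the kind of variable definition that the announced analysis plan is there to give.

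The size of any consequence cannot be derived. Power is 0.994 at alpha 0.05 for the left fusiform signal as powered, and the contrast figures move either way with an assumed correlation. The conclusion rests on two things: that 9.1 and 9.3 are silent on a contrast and do not exclude one, and that the analysis plan is finalised before unblinding as 9.3 requires. It would need revisiting if variable definitions were settled only after treatment was known.
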